6.12. Safety Analyses

Safety measures will include AEs, hypoglycemia, vital signs and weight, treatment exposure, laboratory measures, and antibodies to insulin lispro. Refer to [Table 6.1](#) and [Table 6.2](#) for the analysis population and the baseline definition used in the analysis of a safety measurement for a specific study period.

6.12.1. Extent of Exposure

Duration of exposure to study drug will be summarized. The following summary statistics will be provided: n, mean, SD, median, minimum, maximum, and sum (that is, total patient-years of exposure). The number and proportion of patients falling into the following different exposure categories will also be summarized: <1 month (>0 and <30 days), ≥ 1 and <3 months (≥ 30 and <90 days), ≥ 3 and <6 months (≥ 90 days and <180 days) and ≥ 6 months (≥ 180 days).

Patients who complete the study treatment period are required to complete a safety follow-up visit without study drug; and patients who discontinue the IP prematurely are encouraged to remain in the study without study drug. The days on study after discontinuing IP, and the days on study from date of first study drug to the last study visit date up to Visit 801 will also be summarized.

6.12.2. Adverse Events

Analyses of AEs will include 2 sets of analyses, unless otherwise specified. The first set of analyses will include data collected prior to permanent discontinuation of IP. The second set of analyses will include all data collected during the course of the entire study including the follow-up visit, regardless of IP use.

Events that are newly reported after the first dose of prandial insulin provided as study drug (that is, open-label insulin lispro used during the lead-in period or IP used during the treatment period) or reported to worsen in severity from baseline (defined in [Table 6.2](#) for a specific study period) will be considered TEAEs. The MedDRA Lowest Level Term (LLT) will be used in the treatment-emergent assessment. The maximum severity for each LLT during the baseline period will be used as baseline severity. For events occurring on the day of first dose of bolus insulin provided by this study, the case report form (CRF)-collected flag will be used to determine whether the event started or worsened post-treatment.

In an overview table, the number and percentage of patients who experienced a TEAE, experienced serious adverse event (SAE), died due to an AE, discontinued from study due to an AE, or discontinued IP due to an AE will be summarized by treatment group .

The number and percentage of patients with TEAEs will be summarized by treatment using MedDRA PT nested within SOC. Events will be ordered by decreasing frequency within SOC. As an additional table, the percentages of patients with TEAEs will be summarized by treatment using MedDRA PT (without regard to SOC). Events will be ordered by decreasing frequency. Statistical comparisons will be applied at both the SOC and PT levels. Fisher's exact test will be performed for treatment comparison.

The number and percentage of patients with TEAEs by maximum severity will be summarized by treatment using MedDRA PT (regardless of SOC) and data collected prior to permanent discontinuation of IP. For each patient and TEAE, the maximum severity for the MedDRA PT is the maximum postbaseline severity observed from all associated LLTs mapping to the MedDRA PT. No statistical comparison between treatment groups will be conducted.

The number and percentage of patients with common TEAEs (defined as $\geq 5\%$ before rounding for LY900014-treated patients) will be summarized by treatment group using MedDRA PT (without regard to SOC). Events will be ordered by decreasing frequency. Treatment will be compared by Fisher's exact test.

The number and percentage of patients who experienced an SAE including deaths and SAEs temporally associated or preceding deaths will be summarized by treatment group using MedDRA PT regardless of SOC. Events will be ordered by decreasing frequency. A listing of all SAEs will also be provided.

The number and percentage of patients who discontinued from study due to an AE will be summarized by treatment group using MedDRA (without regard to SOC) using all data regardless of IP use. The number and percentage of patients who discontinued IP due to an AE will be also summarized by treatment group using MedDRA PT (without regard to SOC) using data prior to permanent discontinuation of IP. Events will be ordered by decreasing frequency. A listing of all AEs as reason for study or IP discontinuation will also be provided.

The number and percentage of patients who experienced other notable TEAEs (potential systemic hypersensitivity reaction, injection site reaction, and hepatic disorder) will be summarized by treatment group using all TEAEs regardless of IP use. For events that are gender-specific (as defined by MedDRA), the denominator and computation of the percentage will include only patients from the given gender.

Table 6.5 summarizes the planned analyses and the requirement of analysis data for different analysis periods. A 'Yes' in the IP USE column indicates that only data collected prior to permanent discontinuation of IP will be included.

Table 6.5. Treatment-Emergent Adverse Event Analysis Periods

Analysis Period	Analysis Population	Analysis	IP USE	Treatment
Lead-in Period	All enrolled patients	AE overview; TEAE by PT; SAE, discontinuation due to AE	N/A	Open-label insulin lispro
Treatment Period (0-26 Weeks)	All patients in safety population	AE overview; TEAE by SOC and by PT; common TEAE; TEAEs by maximum severity; SAE; IP discontinuation due to AE	Yes	LY900014, insulin lispro
Week 0 – Visit 801	All patients in safety population	AE overview; TEAE by SOC; common TEAE; SAE; other notable AEs; study discontinuation due to AE	All data regardless of IP use	LY900014, insulin lispro

Abbreviations: AE = adverse event; IP = investigational product; N/A = not applicable/available; PT = Preferred Term; SAE = serious adverse event; SOC = system organ class; TEAE = treatment-emergent adverse event.

6.12.3. Deaths

The listing of all deaths by patient for all enrolled patients will be provided as part of the SAE listing, regardless of the investigator's or the sponsor's judgment about causality. Each listing will include study ID, investigator ID, patient ID, treatment group, baseline age, sex, associated AE, first and last dose date for open label insulin lispro and randomized IP, and the event date.

6.12.4. Hypoglycemic Events and Other Adverse Events

The analysis plans for the following AEs are discussed in Section 6.12.4.1 through Section 6.12.4.4:

- hypoglycemic events
- systemic hypersensitivity reaction
- injection site reaction
- hepatobiliary events

All these AE analyses will be similar to the TEAE analyses, refer to Table 6.5 for the requirement of analysis data for a specific analysis period.

6.12.4.1. Hypoglycemic Events

Hypoglycemia events that occur during the study outside the MMTT will be captured using an eCOA diary starting from Visit 2 through Visit 801. Whenever hypoglycemia is suspected, the patient should record the blood glucose value, any associated symptoms, and the treatment administered in eCOA. A set of events is counted as 1 event in analysis if it consists of an originating event and subsequent continuing events as marked by the patient in eCOA, or the duration between adjacent events is ≤ 30 minutes. The event with the highest severity will be selected for analysis with severity determined in the order of: 1) it is a severe hypoglycemia, 2) it has symptoms of hypoglycemia reported, and 3) it has the lowest blood glucose value. If there are multiple events tied in all 3 aspects, the event with the largest number of non-missing responses to the questions of nocturnal hypoglycemia and postmeal time frame will be selected. If there are still multiple events tied, the latest event (based on data entry time) will be selected.

The following types of hypoglycemia events will be derived in the analysis data sets: documented hypoglycemia, severe hypoglycemia, nocturnal hypoglycemia, probable symptomatic hypoglycemia, and overall hypoglycemia. Only severe hypoglycemia will be collected as AEs and all episodes of severe hypoglycemia will be considered as SAEs. Documented hypoglycemia (including documented symptomatic hypoglycemia, documented asymptomatic hypoglycemia and documented unspecified hypoglycemia) will be based on blood glucose (BG) ≤ 70 mg/dL. In addition, documented clinically significant hypoglycemia with similar criterion as above documented hypoglycemia except for the threshold of BG < 54 mg/dL will be summarized.

Table 6.6 provides detailed statistical methods for each endpoint related to hypoglycemia. For these analyses, hypoglycemia events prior to the discontinuation of IP will be summarized.

Additional analyses for other types of hypoglycemic events not mentioned in the table and for the post-treatment period may be conducted as needed.

The incidence and number of episodes of hypoglycemia during the MMTT will be summarized by treatment and time relative to the meal (≤ 0.5 , ≤ 1 , ≤ 2 , ≤ 4 , >1 to ≤ 2 and >2 to ≤ 4 hours after start of the meal) and analyzed by Fisher's exact test.

A listing of patients with at least 1 severe hypoglycemia reported (as SAE) after randomization will be provided.

A list of MedDRA PTs will be used for the narrow search of potential severe hypoglycemia in spontaneously reported AEs. The events identified through the search strategy that are also reported as SAEs will be summarized and compared between treatments. Fisher's exact test will be used to assess the treatment difference in the proportion of patients with potential severe hypoglycemia.

Table 6.6. Summary of Analyses for Endpoints Related to Hypoglycemia

Endpoint	Analysis Period	Statistical Method
Rate of hypoglycemic events (per patient per 30 days / year) 
 • All Documented^a • Nocturnal^a • Documented Symptomatic^a • Overall • Non-Nocturnal (Documented and occurred between waking and bedtime)^a • Probable Symptomatic 	0-4, 0-12, 0-26, 4-8, 8-12, 12-26 weeks	Negative binomial regression with treatment, and baseline hypoglycemia event rate with the same category of the dependent variable as covariates, log (exposure/30/365.25 days) as the offset in the model.
Incidence of hypoglycemic events 
 • All Documented^a • Nocturnal^a • Documented Symptomatic^a • Overall • Non-Nocturnal (Documented and occurred between waking and bedtime)^a • Probable Symptomatic 	0-4, 0-12, 0-26, 4-8, 8-12, 12-26 weeks	Logistic regression with treatment, baseline hypoglycemia event rate with the same category of the dependent variable as covariates.
Rate of postmeal hypoglycemic events (per patient per 30 days / year) for all 3 main meals 
 • Documented Symptomatic^a • Documented Asymptomatic^a 	≤ 0.5 , ≤ 1 , ≤ 2 , ≤ 4 , >1 to ≤ 2 and >2 to ≤ 4 hours after start of a meal within 0-12,12-26, 0-26 weeks	Negative binomial regression with treatment, baseline postmeal hypoglycemia event rate with the same category of the dependent variable as covariates, log (exposure/30/365.25 days) as the offset in the model.
Incidence of postmeal hypoglycemic events for all 3 main meals 
 • Documented Symptomatic^a • Documented Asymptomatic^a 	≤ 0.5 , ≤ 1 , ≤ 2 , ≤ 4 , >1 to ≤ 2 and >2 to ≤ 4 hours after start of a meal within 0-12,12-26, 0-26 weeks	Logistic regression with treatment, baseline postmeal hypoglycemia event rate with the same category of the dependent variable as covariates.

Summary of Analyses for Endpoints Related to Hypoglycemia

Endpoint	Analysis Period	Statistical Method
Rate of severe hypoglycemic events (per patient per year / 100 years)	0-12, 0-26, 12-26 weeks	Exposure adjusted rate per year / 100 years (calculated by total number of events divided by total exposure for individual patients) will be provided and the empirical method (see Appendix 1 for details) will be used for treatment comparison.
Incidence of severe hypoglycemic events	0-12, 0-26, 12-26 weeks	Proportion of patients with severe hypoglycemia will be reported. The treatment comparison will be based on a logistic regression model with treatment and baseline rate as a covariate.

^a All documented hypoglycemia and the subcategories based on the thresholds of blood glucose ≤ 70 mg/dL and blood glucose < 54 mg/dL will be analyzed, except for postmeal hypoglycemia for which only the threshold of ≤ 70 mg/dL will be applied.

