9.4. Safety

9.4.1. Hypoglycemia

Patients are encouraged to perform SMBG whenever hypoglycemia may be suspected, either by symptoms experienced or perceived increased risk as related to dietary intake, physical activity, or inadvertent or atypical insulin dosing. All patients will be instructed to treat a BG ≤ 70 mg/dL (3.9 mmol/L) as hypoglycemia.

Hypoglycemia events will be collected in eCOA (Section 9.1.4.1). If a hypoglycemia event is suspected, the patient should record the BG value, any associated symptoms, and the treatment administered in eCOA. The patient should contact the site as necessary. Reports of hypoglycemia will be classified by the investigator as “severe” or “not severe” based upon data collected in eCOA and in consultation with the patient, see below and Section 9.2.1. All episodes of severe hypoglycemia must be reported as AEs via electronic data entry, and as SAEs.

Hypoglycemia will be described using the following definitions:

- **Documented hypoglycemia**
 - **Documented symptomatic hypoglycemia:** an event during which typical symptoms of hypoglycemia are accompanied by BG of ≤ 70 mg/dL (3.9 mmol/L);
 - **Documented asymptomatic hypoglycemia:** an event not accompanied by typical symptoms of hypoglycemia but with a BG concentration of ≤ 70 mg/dL (3.9 mmol/L);
 - **Documented unspecified hypoglycemia:** an event during which BG ≤ 70 mg/dL (3.9 mmol/L) but no information relative to symptoms of hypoglycemia were recorded;
- **Probable symptomatic hypoglycemia:** an event during which symptoms are indicative of hypoglycemia and which was presumably caused by BG ≤ 70 mg/dL (3.9 mmol/L) although no BG measurement was reported;
- **Severe hypoglycemia:** An event requiring assistance of another person to actively administer carbohydrate, glucagon, or other resuscitative actions. During these episodes, the patient has an altered mental status and cannot assist in his/her own care, may be semiconscious or unconscious, or experience coma with or without seizures, and may require parenteral therapy. BG measurements may not be available during such an event, but neurological recovery attributable to the restoration of BG concentration to normal is considered sufficient evidence that the event was induced by a low BG concentration (BG ≤ 70 mg/dL [3.9 mmol/L]).

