- **Nocturnal hypoglycemia:** any hypoglycemic event (documented hypoglycemia or probable symptomatic hypoglycemia, including severe hypoglycemia) that occurs between bedtime and waking.
- **Relative hypoglycemia:** an event during which typical symptoms of hypoglycemia, that do not require the assistance of another person, are accompanied by BG > 70 mg/dL (3.9 mmol/L), but these levels may be quickly approaching the 70 mg/dL (3.9 mmol/L) threshold.
- **Overall hypoglycemia:** This category combines all cases of hypoglycemia (documented hypoglycemia and probable symptomatic hypoglycemia, including severe hypoglycemia) excluding the events of relative hypoglycemia. If an event of hypoglycemia falls into multiple subcategories, the event is only counted once in this category.

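### Keeping one record per hypoglycemia set, with symptoms ranked above lowest glucose, can lose a measured low from the documented and <54 mg/dL counts when symptom status is mixed

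*SAP*

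**What the plan says.** SAP 6.12.4.1 defines when several diary records are one event: "A set of events is counted as 1 event in analysis if it consists of an originating event and subsequent continuing events" marked as such by the patient, or "the duration between adjacent events is ≤ 30 minutes". The first route has no time limit.

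One record then stands for the set: "The event with the highest severity will be selected for analysis with severity determined in the order of: 1) it is a severe hypoglycemia", followed by "2) it has symptoms of hypoglycemia reported, and 3) it has the lowest blood glucose value". Remaining ties go to the record with more non-missing answers on nocturnal and postmeal status, and then to the latest entry.

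The kept record is sorted by glucose. Documented hypoglycemia "will be based on blood glucose (BG) ≤ 70 mg/dL", and a clinically significant category uses <54 mg/dL. Footnote a to SAP Table 6.6 says: "All documented hypoglycemia and the subcategories based on the thresholds of blood glucose ≤ 70 mg/dL and blood glucose < 54 mg/dL will be analyzed". Postmeal endpoints are the exception and use ≤70 mg/dL only.

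The categories come from Protocol 9.4.1:
- Symptoms presumed due to low glucose, "although no BG measurement was reported", are probable symptomatic and not documented.
- Typical symptoms with a value above 70 mg/dL are relative hypoglycemia.
- The Overall category is formed "excluding the events of relative hypoglycemia".
- A value ≤70 mg/dL with no symptom information is documented unspecified.

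**The concern.** The ranking is strictly ordered, so lowest glucose decides only between records of equal severe and symptom status. Neither document says that the lowest glucose of the set is attached to the kept record, or that the categories are applied to the set as a whole. A set can therefore contain a qualifying low and still be analysed on a record that fails the glucose criterion.

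Sets of mixed symptom status are foreseeable. Meter values enter the eCOA diary directly (Protocol 9.1.4.1), whereas symptoms depend on a patient entry. The protocol has a category for lows without symptom information, and the SAP revision history treats such events as expected.

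Documented symptomatic hypoglycemia is objective 7 and its postmeal form is objective 6. The <54 mg/dL category is not in a listed objective, but the SAP itself calls it clinically significant. In a comparison of two insulins, undercounting measured lows is the unwelcome direction of error. The lead-in rate, a covariate in these models (SAP 6.2 and Table 6.6), depends on the same derivation.

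**Working it through.** The plan attaches no figure to this rule, so there is none to reproduce. The check applies the rule to specific sets and then to every pattern on a small grid.

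**Three two-record sets**

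| Record 1 | Record 2 (no symptom entry) | Record kept | Lost from | Still counted in |
|---|---|---|---|---|
| Symptoms, no glucose | 60 mg/dL | Record 1: probable symptomatic | All Documented, Documented Symptomatic | Probable Symptomatic, Overall |
| Symptoms, 66 mg/dL | 50 mg/dL | Record 1: documented symptomatic at 66 | <54 mg/dL analysis | All ≤70 counts that apply, Overall |
| Symptoms, 74 mg/dL | 58 mg/dL | Record 1: relative hypoglycemia | All documented categories and Overall | None |

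The third row holds only if relative-hypoglycemia records enter the collapsing step, which SAP 6.12.4.1 neither states nor excludes.

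**Enumeration.** Inputs: non-severe records; symptoms yes, no or not recorded; glucose missing, 45, 50, 60, 65, 75 or 85 mg/dL. A record needs symptoms or a value ≤70 to qualify. The SAP does not say how a missing glucose ranks; it is ranked as the highest value, the reading most favourable to the plan.

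- Record types: 7 with symptoms + 4 with none + 4 with symptoms not recorded = 15. Unordered pairs: 15 × 16 / 2 = 120.
- Sets with a value ≤70: 3 record types have none (symptoms with missing, 75 or 85), giving 3 × 4 / 2 = 6 sets without. 120 − 6 = 114.
- Lost at ≤70: those 3 symptomatic types × 8 non-symptomatic lows = **24 of 114**.
- Sets with a value <54: 9 record types have none, giving 9 × 10 / 2 = 45 sets without. 120 − 45 = 75.
- Lost at <54: 5 symptomatic types (missing, 60, 65, 75, 85) × 4 non-symptomatic values below 54 = **20 of 75**.
- Without relative-hypoglycemia records (75 and 85 removed): 1 × 8 = **8** lost at ≤70 and 3 × 4 = **12** at <54.

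Every loss is in a set of mixed symptom status. These are counts of possible patterns, not expected frequencies.

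**Size under assumptions.** Share lost = (share of episodes with several records) × (share of those where the qualifying low sits only on a record without symptoms). Assuming 5% to 30% for the first and 10% to 50% for the second:
- lowest: 0.05 × 0.10 = 0.5%
- highest: 0.30 × 0.50 = 15%

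**Effect on a rate ratio.** With qT and qC the shares lost on LY900014 and insulin lispro, the true ratio is multiplied by (1 − qT)/(1 − qC):
- equal loss: 1.00
- 10% versus 5%: 0.90/0.95 = 0.947
- 5% versus 10%: 0.95/0.90 = 1.056

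**Alternatives.** Classifying the set on any symptoms and lowest glucose loses a ≤70 or <54 reading in 0 of 120 sets. Swapping the second and third criteria does not solve the problem: it drops the symptom flag in 36 of 120 sets.

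**The case against.** The rule has a purpose. Ranking symptoms first protects the symptomatic endpoints, as the 36 sets above show. Severe events rank first, so objective 5 is safe. Patients are told to record glucose, symptoms and treatment together, so split records depart from instruction and may be uncommon. This stands as a limit on size, but it does not repair the count when a split set occurs.

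Protocol 9.4.1 asks for symptoms accompanied by a value ≤70 mg/dL. One can dispute whether symptoms on one record and a low on another meet that, especially in patient-marked sets with no time limit. That caution is fair for Documented Symptomatic. It does not explain losing the low from All Documented, which needs no symptoms, and the SAP already treats the records as one event.

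Three stronger readings are tempting and are not supported:
- A reader might infer that measured lows generally vanish from the hypoglycemia endpoints. The loss is conditional, and in the first two examples the episode stays in Overall or in the ≤70 counts. Only the third leaves everything, and it rests on the unstated handling of relative-hypoglycemia records.
- A reader might infer a bias favouring LY900014. The rule is the same in both arms of a double-blind trial. The documents give no loss share by arm, and unequal loss could move the ratio either way.
- A reader might infer that every count can only fall. This holds for totals by glucose threshold but not for the postmeal windows in Table 6.6. With 65 mg/dL and no symptoms at 55 minutes, then symptoms at 62 mg/dL at 70 minutes, keeping the second record places the event in the window from over 1 to 2 hours.

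**Conclusion.** The point holds in conditional form. As written, the rule loses a measured low when a set has mixed symptom status and the symptomatic record has no glucose or a value above the cut-off. Compared with classifying the whole set, total counts by glucose threshold can only be understated. This is a stated rule that gives a wrong count, not missing detail.

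The size is unknown. The 0.5% to 15% range rests entirely on assumed shares, and the certain effect is an undercount rather than a distorted comparison. SAP 6.5 makes no multiplicity adjustment beyond the primary and multiplicity adjusted objectives, so objectives 6 and 7 are outside the alpha-controlled family and the HbA1c and PPG excursion tests are untouched. The change should be made because it is cheap and concerns safety counts; the trial's main conclusion does not depend on it.

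**What to change.** Before unblinding, amend SAP 6.12.4.1 as follows.

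1. Keep one event per set, but classify the set: severe if any record is severe, symptomatic if any record reports symptoms, glucose equal to the lowest non-missing value. Then apply the ≤70 and <54 mg/dL categories.
2. Take nocturnal and postmeal status from the records with non-missing answers, in line with the existing tie-break. Do not use the originating record alone: the SAP revision history says meal timing is missing for documented unspecified events, so a set opening with such a record would drop out of objective 6.
3. State whether relative-hypoglycemia records enter the collapsing step.
4. Use the same derivation for the lead-in baseline rate.

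The cost is a few lines of SAP text and a small programming change on data already collected. Reported rates would be slightly higher. If set-level classification is already intended, one sentence saying so settles the main point.

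### SAP Table 6.6 appears to restrict nocturnal hypoglycemia to events with a measured glucose value, whereas the protocol also counts probable and severe night-time events without one

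*SAP*

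**What the plan says.** Protocol 9.4.1 counts as nocturnal "any hypoglycemic event (documented hypoglycemia or probable symptomatic hypoglycemia, including severe hypoglycemia) that occurs between bedtime and waking". Two of the components can lack a glucose value. A probable symptomatic event is one recorded "although no BG measurement was reported". For a severe event, "BG measurements may not be available during such an event".

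SAP 6.12.4.1 names the event types to be derived: "documented hypoglycemia, severe hypoglycemia, nocturnal hypoglycemia, probable symptomatic hypoglycemia, and overall hypoglycemia". Nocturnal is a type of its own in that list, and the readable SAP does not redefine it.

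In SAP Table 6.6 the rate and incidence blocks list six categories. Four carry footnote a: *All Documented*, *Nocturnal*, *Documented Symptomatic* and *Non-Nocturnal*. Two do not: *Overall* and *Probable Symptomatic*. The footnote begins "All documented hypoglycemia and the subcategories based on the thresholds of blood glucose" and gives the thresholds as at or below 70 mg/dL and below 54 mg/dL. The daytime row is labelled "Non-Nocturnal (Documented and occurred between waking and bedtime" (closing bracket omitted here). The *Nocturnal* label has no such qualifier. Severe events have separate rate and incidence rows without the footnote.

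**The concern.** The table seems to treat nocturnal hypoglycemia as a subcategory of documented hypoglycemia, although the protocol defines it more broadly. If so, a severe night-time event in which nobody took a reading is counted as severe and as overall hypoglycemia, but not as nocturnal. The reported nocturnal rate and incidence would then describe a narrower category than the one the protocol names.

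The text is also open enough that two programmers could build different nocturnal datasets from it. The model covariate inherits the ambiguity, because Table 6.6 adjusts each analysis for the baseline rate in the same event category.

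**Working it through.** The plan states no figure on this point, so the check compares the texts and then illustrates the effect with assumed shares.

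**1. What the protocol requires.** Under Protocol 9.4.1, nocturnal = (documented, probable symptomatic or severe) and overnight. Protocol 10.3.4 then plans rate and incidence models for each hypoglycemia category other than severe.

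**2. What footnote a requires.** Each documented type in Protocol 9.4.1 is defined by a glucose value at or below 70 mg/dL. SAP 6.12.4.1 uses the same threshold and adds a documented clinically significant version below 54 mg/dL. The pattern of marks in Table 6.6 fits a measured value: every marked row other than *Nocturnal* has the word documented in its label, while the rows that take in events without a reading (*Overall*, *Probable Symptomatic*, severe) are unmarked.

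**3. Below 54 mg/dL.** An event without a reading cannot qualify. Where the protocol presumes or accepts a low value, it does so only at the 70 mg/dL level. Exclusion is certain.

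**4. At or below 70 mg/dL.** Exclusion follows only if the footnote demands a measured value. The protocol describes a probable event as one where "symptoms are indicative of hypoglycemia and which was presumably caused by BG" at or below 70 mg/dL. For a severe event without a reading, it says that neurological recovery "is considered sufficient evidence that the event was induced by a low BG concentration" at that level. Such events could therefore be placed in the class by presumption. Exclusion is the likelier reading but is not stated.

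**5. Merged episodes.** SAP 6.12.4.1 combines linked events, or events no more than 30 minutes apart, and keeps one record: severe first, then symptomatic, then lowest glucose. A symptomatic night-time event without a reading outranks an asymptomatic low reading taken minutes later. On the measured-value reading, that episode could also leave the nocturnal row unless the reading is carried over, and the SAP does not say that it is.

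**6. Size (assumed shares; the documents give none).** Let u be the share of protocol-defined nocturnal events without a reading.

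- Rate on the measured-value reading = protocol-defined rate × (1 − u). For u = 5%, 10% and 20% the factors are 0.95, 0.90 and 0.80.
- Rate ratio on the measured-value reading = protocol-defined ratio × (1 − u for LY900014) / (1 − u for insulin lispro).
  - Equal shares: factor 1, no change.
  - 5% against 10%: 0.95/0.90 = 1.06; with the arms reversed, 0.90/0.95 = 0.95.
  - 10% against 20%: 0.90/0.80 = 1.13; with the arms reversed, 0.80/0.90 = 0.89.
- Incidence falls only through patients whose nocturnal events in the period all lack a reading. That cannot be derived from u.

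**7. Justification.** SAP 6.1 says that changes to protocol methods, with reasons, will be described in the SAP and/or the study report. The SAP revision history explains which postmeal hypoglycemia summaries were dropped and why. The readable text says nothing about narrowing nocturnal.

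**The case against.** The best defence is that the SAP never says nocturnal means documented-only. It lists nocturnal as a separate type, leaves the protocol definition as the only one available, and writes the restriction out for the daytime row but not for the night-time row. On that view footnote a merely adds threshold-based versions. This stands as a possible reading, and it is why exclusion at or below 70 mg/dL cannot be asserted as fact. It does not settle the matter: the footnote's own words and the pattern of marked rows point the other way, and nothing tells a programmer how to class an event without a reading.

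The defence also notes that the protocol has no nocturnal category below 54 mg/dL, so omitting unmeasured events there breaks no protocol commitment. That is correct. The conflict with the protocol lies in the absence of a clearly protocol-defined nocturnal row.

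A reader might infer three stronger things, none of which the documents support:

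- *That these events vanish from the safety analysis.* They do not. They remain in *Overall*, and in *Probable Symptomatic* or the severe rows. Severe events are also reported as SAEs, with a patient listing and narratives.
- *That the Non-Nocturnal row is itself wrong, or that one of the two rows must be.* The protocol does not define non-nocturnal, neither document requires the two rows to add up, and a documented daytime row removes no night-time event. If *Nocturnal* follows the protocol, the two rows simply differ in scope.
- *That the treatment comparison is biased, or that unmeasured readings are especially common in severe events.* No figure supports either. The trial is double-blind and both arms use the same electronic diary, so the documents give no reason to expect the share to differ by arm.

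**Conclusion.** The point holds in limited form. Table 6.6 with footnote a does not clearly implement the protocol's definition of nocturnal hypoglycemia, and the readable SAP gives no reason for the difference. Exclusion of events without a glucose value is certain below 54 mg/dL and likely, but not explicit, at or below 70 mg/dL.

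Only the nocturnal rate and incidence are affected. On the measured-value reading the rate is understated by the share of nocturnal events without a reading. That share is not in the documents, so the 5% to 20% values above are illustrations and not estimates.

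The hypoglycemia objectives are severe, documented symptomatic postmeal and documented symptomatic events (objectives 5 to 7). Nocturnal hypoglycemia is not among the primary, multiplicity-adjusted or other secondary endpoints. Priority is minor.

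**What to change.** In SAP Table 6.6:

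1. Remove footnote a from *Nocturnal* and state that the row follows Protocol 9.4.1, so that probable and severe overnight events count whether or not there is a reading.
2. Label the threshold-based rows *Documented nocturnal*, at or below 70 mg/dL and below 54 mg/dL. These then pair with the existing documented *Non-Nocturnal* row.
3. Optionally, add a *Non-Nocturnal* row covering all event types, to pair with the row in step 1.

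The events are already captured in the diary, so no new data are needed. If the table now implies two threshold versions of *Nocturnal*, step 1 adds one category: 1 category × 6 periods × 2 models (rate and incidence) = 12 further analyses. Step 3 would add another 12. The downside is these extra output rows, with no multiplicity adjustment planned for them.
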